6.0 Study Treatment Duration and Compliance

Unless otherwise stated, parameters in this section will be summarized for the DBP and BEP, respectively. The safety population and BEP population will be used for the DBP

and BEP, respectively. For parameters during the BEP, first and last dose dates are the ones during the BEP.

Duration of treatment (days) is defined for each subject as follows:

$$\text{Duration of treatment (days)} = \text{last dose date} - \text{first dose date} + 1$$

Duration of treatment will be summarized for each treatment group (modal daily dose for BEP) and each period using the number of subjects treated, mean, standard deviation, median, minimum and maximum. In addition, the number and percentage of subjects in each treatment duration interval (1, 2 to 7, 8 to 14, 15 to 21, 22 to 28, 29 to 35, 36 to 42 and > 42 days for the DBP, 1, 2 to 14, 15 to 28, 29 to 42, 43 to 56, 57 to 70, 71 to 84, 85 to 98, 99 to 112, 113 to 126 and > 126 days for the BEP) will be summarized.

Patient-years, defined as exposure to study drug in years, will be summarized by treatment group (modal daily dose for BEP).

$$\text{Patient - years} = \frac{\text{Sum of treatment duration of all subjects (days)}}{365.25}$$

Overall mean daily dose of study drug will be summarized by treatment group (modal daily dose for BEP) and period. For DBP, placebo will not be summarized. In addition, final daily dose of study drug will be summarized by modal daily dose for the BEP.

Treatment compliance (TC) (%) will be summarized by treatment group (modal daily dose for BEP) using descriptive statistics. Treatment compliance for a specified period is defined as the number of capsules actually taken divided by the number of capsules that should have been taken multiplied by 100 as follows:

$$\text{TC (\%)} = \frac{\text{Total number of capsules taken}}{(\text{last dose date} - \text{first dose date} + 1) \times \text{number of capsules per day}} \times 100$$

Percent compliance and its categories (< 80, 80 to 100) will be summarized.

7.0 Subject Characteristics

Categorical variables will be summarized with the number and percentage of subjects; percentages will be calculated based on the number of non-missing observations.

Continuous variables will be summarized with descriptive statistics (number of non-missing observations, mean and standard deviation, median, minimum, and maximum).

7.1 Definitions of Baseline and Baseline Derived Variables

Unless otherwise specified, baseline is defined as the last non-missing value prior to the first administration of study drug for the DBP. For efficacy variables, baseline is defined as the non-missing value recorded at Visit 2.

7.1.1 Disease Duration

Disease duration (years) is defined for each subject as follows:

$$\begin{aligned} \text{Disease duration (years)} \\ = & \text{ (date of informed consent} \\ & - \text{ date of initial diagnosis of schizophrenia + 1) / 365.25} \end{aligned}$$

7.1.2 Time Since Exacerbation

Time since exacerbation (days) is defined for each subject as follows:

$$\begin{aligned} \text{Time since exacerbation (days)} \\ = & \text{ date of informed consent} \\ & - \text{ Onset date of current psychotic episode of schizophrenia exacerbation + 1} \end{aligned}$$

7.2 Demographics and Baseline Characteristics

Demographics and baseline will be summarized descriptively, overall and by treatment group for the Safety and mITT populations, respectively. Medical history, procedure history, psychiatric history (disease duration and time since exacerbation), antipsychotic drug history, and nondrug psychiatric treatment history will also be summarized by treatment group.

Continuous demographic variables include age, weight, height and body mass index (BMI).

Continuous baseline variables include SCI-PANSS total score, SCI-PANSS positive symptom score, 16-Item Negative Symptom Assessment (NSA-16) total score, SCI-PANSS negative symptom score, SCI-PANSS negative factor score, disease duration and time since exacerbation.

Categorical demographic variables include:

- Sex (Male, Female)
- Ethnicity (Hispanic or Latino, Not Hispanic or Latino)
- Race (Asian (Japanese, Non- Japanese), Other (specify))
- Region (Japan or Taiwan)
- Age (< 40 or \geq 40 years)
- Weight (< 60 or \geq 60 kg)
- BMI (< 25 or \geq 25 kg/m²)
- Smoking history (current, former, never, unknown)

Categorical baseline variables include:

- Medical history (Yes, No)
- Procedure history (Yes, No)
- Number of antipsychotic drug (0, 1, 2)

7.3 Medical History and Prior and Concomitant Medications

Medical history data will be coded using the Medical Dictionary for Regulatory Activities (MedDRA). The actual version of the MedDRA coding dictionary will be noted in the statistical tables and clinical study report. The number and percentage of subjects in each medical history category (by MedDRA system organ class (SOC) and preferred term) will be summarized overall and by treatment group for the safety population. The SOC will be

presented in alphabetical order, and the preferred terms will be presented in alphabetical order within each SOC. Subjects reporting more than one condition/diagnosis will be counted only once in each row (SOC or preferred term).

Prior and concomitant medications will be summarized separately. The number and percentage of subjects taking prior medications for the DBP will be summarized by treatment group and generic name for the safety population. The number and percentage of subjects taking concomitant medications for the DBP and BEP will be summarized by treatment group (modal daily dose for BEP), Anatomical Therapeutic Chemical (ATC) code level 2 and generic drug name for the safety population and BEP population, respectively. Generic name will be based on the World Health Organization (WHO) Drug Dictionary. The actual version of the WHO Drug Dictionary will be noted in the statistical tables and clinical study report.

A prior medication is defined as any medication taken prior to the date of the first dose of study drug. A concomitant medication during the DBP and BEP is defined as any medication taken on or after the start of study drug for the DBP and BEP, respectively.

Prior antipsychotic drug will be summarized by treatment group and generic drug name for the safety population.

The use of rescue medications during the DBP and BEP will be summarized by treatment group (modal daily dose for BEP) and generic drug name for the safety population and BEP population, respectively.

If a subject took a specific medication multiple times or took multiple medications within a specific generic drug name, that subject would be counted only once for the coded drug name. Any medications started after the last dose of study drug will not be summarized but will be included in listings.

7.4 Protocol Deviations

For each of the following protocol deviation categories and across all categories, the number and percentage of randomized subjects with at least one protocol deviation will be summarized overall and by treatment group:

- Subject entered into the study even though did not satisfy entry criteria;
- Subject developed withdrawal criteria during the study but was not withdrawn;
- Subject received wrong treatment or incorrect dose of study treatment;
- Subject took prohibited concomitant medication.

8.0 Handling of Potential Intercurrent Events for Efficacy Endpoints

The potential intercurrent events are use of rescue medications and discontinuation of study drug in the analyses for efficacy endpoints.

Regardless of whether rescue medications are used, data are included in the analyses. Data after discontinuation of study drug will not be included in the analyses and will be assumed missing at random. Data on the same day of discontinuation from treatment as the last dose will be included in the analyses.

9.0 Efficacy Analyses

9.1 General Considerations

Due to the low number of randomized patients, for all efficacy endpoints, the descriptive statistics including mean difference between cariprazine group and placebo group will be provided by treatment group using the last observation carried forward (LOCF) approach or the observed case (OC) approach, respectively unless otherwise stated. Detailed definition on the approach is specified in Section 9.2.1. The statistics include number of observations, mean, standard deviation, minimum, median, and maximum for continuous variables, and number and percent for discrete variables. The 2-sided 95% confidence

interval (CI) will be provided for the difference between cariprazine group and placebo group. In addition, figures for mean/standard deviation of primary and secondary continuous endpoints will be presented by treatment group using the LOCF approach or the OC approach. No statistical tests will be performed for comparison with placebo group.

The descriptive statistics and figures for all efficacy endpoints in BEP will be also provided by modal daily dose using the LOCF approach or the OC approach.

The efficacy analyses during the DBP and BEP will be based on the mITT population and BEP population, respectively. "Baseline" for efficacy is defined as the non-missing value recorded at Visit 2, before the first dose of study drug for the DBP as described in Section 7.1.

In principle, for all efficacy endpoints, the analysis during DBP for comparison with placebo group will be additionally performed based on the pooled cariprazine group.

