7.4 Statistical Analyses for Efficacy

Summary and Analysis of the Primary Endpoint

Analysis of the primary endpoint (change from baseline to DBP Week 6 in SCI-PANSS total score) will be conducted on the mITT population based on treatment as randomized. The primary analysis will be performed using the observed postbaseline change from baseline scores during the DBP through a mixed model for repeated measures (MMRM) with treatment, study center, visit, treatment-by-visit interaction as the fixed effects, and the baseline value and baseline-by-visit interaction as covariates. An unstructured covariance matrix will be used to model the within-subject covariance. If the models fail to converge, the compound symmetry covariance matrix will be used instead. The Kenward-Roger approximation will be used to estimate the denominator degrees of freedom.

Summary and Analysis of Secondary Endpoints

Summary and Analysis of Key Secondary Endpoint

Analysis of the key secondary endpoint, change from baseline to DBP Week 6 in CGI-S, will be analyzed using the same MMRM model as the primary endpoint.

Subgroup Analysis for Efficacy

Subgroup analyses of the primary endpoint will be conducted for the following subgroups:

- Age category (< 40 years or \geq 40 years)
- Sex (male or female)
- Region (Japan or Taiwan)

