9.3 Primary Efficacy Endpoint and Analyses

9.3.1 Primary Efficacy Endpoint

The primary endpoint for the primary analysis of efficacy is:

- Change in SCI-PANSS total score from baseline to DBP Week 6.

The SCI-PANSS total score will be derived as the sum of the 30 items (P1-P7, N1-N7, and G1-G16) of SCI-PANSS, using this formula: (total number of items in the scale) \times (sum of non-missing items divided by number of items with non-missing values). If more than 3 items for the SCI-PANSS total score are missing, the total score will be set to missing.

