9.4 Secondary Efficacy Endpoints and Analyses

9.4.1 Key Secondary Efficacy Endpoint for DBP

The key secondary endpoint of efficacy is:

- Change in Clinical Global Impression-Severity (CGI-S) score from baseline to Week 6

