9.4.4 Additional Efficacy Endpoints and Analyses

The additional efficacy endpoints for DBP are:

- PANSS responder (subjects with SCI-PANSS total score improved by $\geq 30\%$ at Week 6 compared with Baseline)

For the PANSS responder, the number, percent and 2-sided 95% CI will be provided using the LOCF approach, the OC approach or the NRI approach, respectively. Details on the analysis, output are specified in Section 9.1 and Section 9.2.2.

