13.1 Changes to Planned Analyses in the Protocol

- No interim database lock for primary analysis will be conducted and a database lock will occur after the evaluation of all enrolled subjects in BEP has been completed.
- The cariprazine 3 mg/day group will be included for all efficacy and safety analysis in the DBP.
- Target sample size for statistical power is 250 subjects, however actual number of randomized subjects will be 34 subjects.

- For all efficacy endpoints in the DBP, the descriptive statistics for continuous variables will be provided using several approaches for missing data, and the number and percent for discrete variables as well. The 2-sided 95% confidence interval (CI) will be provided for the difference between cariprazine group and placebo group. In addition, figures of mean/standard deviation for primary and secondary continuous variables will be presented using several approaches for missing data. The descriptive statistics and figures for all efficacy endpoints in BEP will be also provided using several approaches for missing data.
- No statistical tests and no model analysis will be performed for comparison with placebo group and the control of type I error rate will not be considered.
- The analysis for comparison between the pooled cariprazine group and placebo group will be performed.
- Subgroup efficacy analyses for PANSS total score at Baseline and Negative symptom at Baseline will be performed.

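### SAP v3.0 drops the baseline covariate, so the cariprazine-placebo differences in mean change are not adjusted for regression to the mean after a chance baseline imbalance; a descriptive ANCOVA column would cover this at little cost

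*SAP*

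**What the plan says.** Protocol 7.4 specifies an MMRM for the primary endpoint that includes "the baseline value and baseline-by-visit interaction as covariates", and applies the same model to CGI-S.

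SAP v3.0 replaces this after early termination. Section 9.1 cites the low number of randomized patients and provides that "the descriptive statistics including mean difference between cariprazine group and placebo group will be provided by treatment group", under LOCF and OC. Sections 9.3.2, 9.4.2 and 9.4.3 repeat the approach for the primary, key secondary and additional secondary endpoints. Section 13.1 declares the change: "No statistical tests and no model analysis will be performed for comparison with placebo group". It keeps an interval: "The 2-sided 95% confidence interval (CI) will be provided for the difference between cariprazine group and placebo group".

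The endpoints compared are changes from baseline, for example "Change in SCI-PANSS total score from baseline to DBP Week 6" and "Change in Clinical Global Impression-Severity (CGI-S) score from baseline to Week 6".

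Two groups of efficacy endpoints fall outside this point because no cariprazine-placebo mean difference is reported for them:
- The responder endpoint (SAP 9.4.4): "For the PANSS responder, the number, percent and 2-sided 95% CI will be provided".
- The extension-period endpoints (SAP 9.1 and 9.4.5): "The descriptive statistics and figures for all efficacy endpoints in BEP will be also provided by modal daily dose". That period has no placebo arm.

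**The concern.** With so few subjects, the arms can differ noticeably in mean baseline severity by chance. SAP 2.3 stratifies randomization by site only, so the design does not balance baseline score.

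Using a change score removes an imbalance completely only if the Week 6 score rises one point for each point of baseline. If the slope is smaller, subjects who start higher tend to fall further, and the arm with the higher baseline appears to improve more. The protocol's model would have allowed for this and SAP v3.0 does not.

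A small sample is a fair reason to give up an MMRM with study center, visit interactions and an unstructured covariance matrix. It is not a reason to give up a single covariate. The differences and intervals are the only between-arm efficacy results for these scales, so it is worth knowing how far a baseline imbalance could move them.

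**Working it through.** **Inputs from the documents.** Randomized N = 34 (SAP 1.0). Planned difference -8.3, SD 20 at Week 6, 125 per arm (SAP 2.4). Baseline PANSS total between 80 and 120 (protocol 5.1, criteria 10 and 11). The 3 mg/day arm is included (SAP 13.1), so the 34 may be spread over three arms.

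**Assumptions, not in the documents.** Per-arm n from 11 (about equal thirds) to 17 (no one on 3 mg/day). Baseline PANSS SD from 8 to 11; a uniform spread over 80 to 120 would give 40/√12 = 11.5. Slope γ of change on baseline from -0.2 to -0.5.

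**1. The plan's own figure.** SE = 20 × √(2/125) = 2.53, and 8.3/2.53 = 3.28. Power ≈ Φ(3.28 - 1.96) = 0.907. This agrees with the stated 90% or more, so SD 20 is used below as the SD of change. The dropout and correlation inputs are not given, so the MMRM version cannot be checked.

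**2. What passes through.** Let b be the slope of Week 6 score on baseline and d the difference in mean baseline between arms. Given d, the difference in mean change is shifted by (b - 1) × d = γ × d. Nothing passes if b = 1, and all of d passes if b = 0. With γ from -0.2 to -0.5, 20% to 50% passes.

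**3. Size of the shift, PANSS total.** SD of d = SD_baseline × √(2/n). The 95% limits of d are ±1.96 times that, and the limits of the shift are |γ| times the limits of d.

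| n per arm | Baseline SD | SD of d | 95% limits of d | Shift, γ = -0.2 | Shift, γ = -0.5 |
|---|---|---|---|---|---|
| 17 | 8 | 2.74 | ±5.4 | ±1.1 | ±2.7 |
| 17 | 11 | 3.77 | ±7.4 | ±1.5 | ±3.7 |
| 11 | 8 | 3.41 | ±6.7 | ±1.3 | ±3.3 |
| 11 | 11 | 4.69 | ±9.2 | ±1.8 | ±4.6 |

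**4. Against the interval that will be reported.** Half-width = t(0.975, 2n - 2) × 20 × √(2/n).
- 17 per arm: 2.037 × 6.86 = 13.97.
- 11 per arm: 2.086 × 8.53 = 17.79.

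The limiting shifts are about 8% (1.1/13.97) to 26% (4.6/17.79) of the half-width.

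**5. Width after adjustment, PANSS total.** The correlation of change with baseline is r = γ × SD_baseline/20, from -0.08 to -0.275, so r² runs from 0.6% to 7.6%. In a two-arm ANCOVA with N = 2n, the half-width is t(0.975, N - 3) × 20 × √(1 - r²) × √(2/n) × √(1 + 1/(N - 4)).
- 17 per arm, SD 11, γ = -0.5: 13.67, ratio 0.98.
- 11 per arm, SD 8, γ = -0.2: 18.28, ratio 1.03.
- 11 per arm, r = 0: 18.34, ratio 1.03.

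The width therefore changes by about -2% to +3%.

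**6. Width on a scale with equal baseline and Week 6 SDs.** With baseline-to-Week-6 correlation ρ, the residual SD ratio of ANCOVA to change score is √((1 - ρ²)/(2(1 - ρ))) = √((1 + ρ)/2), which is 0.84 at ρ = 0.4 and 0.92 at ρ = 0.7. With the degrees-of-freedom and estimation penalties of step 5, the width ratios are 0.86 and 0.95 at 11 per arm, and 0.85 and 0.94 at 17 per arm. The CI is about 5% to 15% narrower.

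**The case against.** The strongest objection is that this is a declared, reasoned choice for an abbreviated report with no tests and no type I error claim, and that a plain descriptive summary is legitimate. That stands: SAP 13.1 lists the change openly, and nothing here is an error of inference.

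A reader might go further and infer any of the following. The documents do not support them.
- **That a baseline imbalance enters the difference in full.** Each subject's baseline is already subtracted. Only the fraction in step 2 remains.
- **That every efficacy endpoint is affected.** The responder and extension-period summaries contain no cariprazine-placebo mean difference.
- **That the reported CI is invalid.** Under randomization its width already allows for chance imbalance on average.
- **That the result could be off by half the planned effect.** The 4.6-point limit is 55% of 8.3, but it needs the smallest arms, widest baseline SD, steepest slope and a 1.96-SD imbalance together. It still lies well inside the interval.

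It is also true that on these inputs baseline explains at most 7.6% of the variance of change in PANSS total, so most of the chance error would remain after adjustment. The 5% to 15% gain on other scales rests on assumed correlations.

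Finally, SAP 7.2 tabulates baseline PANSS scores and NSA-16 by arm, and 9.5 splits the primary endpoint at a baseline of 100. These tables would show an imbalance in those scores, although CGI-S is not in the 7.2 list. None of them gives an adjusted difference.

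**Conclusion.** The point holds as a modest, inexpensive improvement. SAP v3.0 leaves no baseline-adjusted efficacy estimate, and the small sample does not rule out one covariate. For PANSS total the benefit is protection of the point estimate against the shift in step 3; the gain in precision is about nil. For scales resembling step 6 there may also be a useful gain in precision.

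The size depends on per-arm counts, baseline SDs, slopes and correlations that the documents do not give. The OC analysis may use fewer subjects than the 34 randomized, which would widen both the shift and the interval. The statement that the raw difference is unbiased concerns the concurrently randomized 6 mg/day and placebo arms. Comparisons that use the withdrawn 3 mg/day arm raise a separate question, not examined here.

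**What to change.** In SAP 9.1, 9.3.2, 9.4.2 and 9.4.3, keep the raw means, raw difference and its CI. Beside them add the Week 6 difference and 95% CI from an ANCOVA of change on treatment and the baseline value of the same scale, for both LOCF and OC data, with no p-value. Specify two models:
- One with placebo, 3 mg/day and 6 mg/day as treatment levels, giving the by-dose differences from placebo.
- One with pooled cariprazine versus placebo.

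Amend the statement in SAP 13.1 that excludes model analysis so that it allows this descriptive adjustment. The estimand summary, a difference in means, does not change, and neither does the decision not to test.

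The cost is SAP wording, one degree of freedom for the covariate and one table column. If baseline is nearly unrelated to change, the adjusted CI may be up to about 3% wider than the raw one.

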APPENDIX E. PROTOCOL SUMMARY OF CHANGES

Previous Protocol Versions

Protocol	Date
Version 1.0	27 January 2022
Version 2.0	15 February 2023

The purpose of this version is to correct minor clerical errors for consistency throughout the protocol in addition to the following necessary protocol modifications:

- To simplify the design of the DBP, the cariprazine 3 mg/day treatment arm was removed from the DBP and the total number of subjects to be randomized to treatment in the DBP was reduced.
 - Section 1 and Section 4.1 – modified to:
 - remove the cariprazine 3 mg/day treatment arm from the DBP
 - update the number of subjects to be enrolled from 402 subjects (134 per treatment arm) to 250 subjects (125 per treatment arm)
 - clarify that subjects will be randomized in a 1:1 ratio to placebo or cariprazine 6 mg/day for the DBP
 - clarify that subjects who complete the DBP and opt to enter the BEP will be switched to the following treatment at Week 6 (Visit 8): subjects who received placebo during the DBP will be switched to cariprazine 1.5 mg/day, and subjects who received cariprazine 6 mg/day during the DBP will receive cariprazine 3 mg/day in a blinded manner
 - revise the approximate number of study sites
 - **Figure 1** – modified to remove the cariprazine 3 mg/day treatment arm in the DBP and add a footnote to reference the DBP titration schedule in **Table 1**, and to clarify that subjects who received cariprazine 6 mg/day during the DBP will receive cariprazine 3 mg/day in a blinded manner at Week 6 (Visit 8)
 - **Table 1** – modified to remove the cariprazine 3 mg/day treatment arm from the DBP
 - Section 4.2 – modified to remove mention of the cariprazine 3 mg/day treatment group from the DBP
- Eligibility criterion #6 and **Appendix D** were modified to allow the alcohol screening test (Visit 1) to be performed using either a blood or urine test.
- Lemborexant was added to eligibility criteria #10 and #42 to clarify washout requirements.
- Eligibility criterion #32 was modified to clarify criteria to follow for a symptomatic subject infected with SARS-CoV-2.
- Section 5.5 and Section 5.7 – removed reference to direct-to-patient shipping of study drug because this service is no longer available.

- Section 6.1 – clarified that all AEs reported from the time of study drug administration until 8 weeks after discontinuation of study drug administration will be collected, whether solicited or spontaneously reported by the subject.

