1.0 Introduction

This Statistical Analysis Plan (SAP) describes the methodology that will be used to summarize the statistical analyses of the efficacy and safety data for cariprazine Study M22-509's original protocol (version 1.0, 27Jan2022) and its most recent amendment (version 3.0, 25Jul2023).

The analyses pharmacokinetics (PK) endpoints will be analyzed separately and will not be covered in this SAP.

The Study M22-509 was early terminated as result of discussion due to an unexpected delay in enrollment. The main reasons for slow enrollment may include changes in the treatment environment with fewer relapses and exacerbations, difficulty obtaining informed consent due to washout of current antipsychotics during hospitalization, and the COVID-19 pandemic. Despite several protocol amendments to improve progress, approximately 30 subjects were enrolled (target: 250 subjects). 34 subjects were finally randomized at the time of early termination. The SAP will be part of the abbreviated CSR.

Unless noted otherwise, all analyses will be performed using SAS Version 9.4 (SAS Institute Inc., Cary, NC 27513) or later.

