2.4 Sample Size Determination

In terms of the change from baseline in the SCI-PANSS total score at Week 6, the sample size of 125 subjects per arm (N = 250) can achieve at least 90% power at overall 0.05 two-sided significant level to detect the statistically significant difference between placebo and cariprazine 6 mg/day based on these assumptions using a Mixed-Effect Model for Repeated Measurement (MMRM); treatment difference of -8.3 between 6 mg/day and placebo based on the full analysis set (FAS) 2 in Studies A002-A4 and RGH-MD-04, and common standard deviation of 20 at Week 6 taking into account dropout rates and correlation matrix based on FAS in Study A002-A4.

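### The descriptive 3 mg and pooled cariprazine differences use placebo subjects from both randomisation stages, so a shift in outcome between stages would enter them (minor)

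*SAP*

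**What the plan says.** Protocol Appendix E records that the current version removed the 3 mg/day arm from the double-blind period. Its entry reads "update the number of subjects to be enrolled from 402 subjects (134 per treatment arm) to 250 subjects (125 per treatment arm"; I cite it only as evidence of the preceding design, which had three equal arms. Protocol 5.8 and SAP 2.3 now randomise 1:1 to placebo or 6 mg/day, stratified by site according to SAP 2.3.

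Protocol 7.1 left the 3 mg subjects out of the double-blind analyses. The SAP reverses this openly in section 2.2 and again in 13.1: "The cariprazine 3 mg/day group will be included for all efficacy and safety analysis in the DBP". SAP 9.1 adds that "the analysis during DBP for comparison with placebo group will be additionally performed based on the pooled cariprazine group".

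Under SAP 9.1 and 13.1 the results are mean differences from placebo with two-sided 95% confidence intervals, with no model and no tests. SAP 4.0 and 9.1 make the mITT population the basis. Read together, these sections give a 3 mg, a 6 mg and a pooled difference, each against the same full placebo group. No section limits placebo to subjects randomised while the 3 mg arm was open, stratifies by stage, or mentions the issue as a limitation.

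**The concern.** Call the period under the three-arm schedule stage 1 and the period under the two-arm schedule stage 2. Every 3 mg subject belongs to stage 1, while placebo subjects can come from either. Stage is therefore associated with treatment by design, both for 3 mg versus placebo and for pooled cariprazine versus placebo. If mean PANSS change differs between stages for reasons unrelated to treatment, part of that difference appears as a treatment effect. The confidence interval will not show it, because the interval reflects sampling error only.

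A shift between stages is possible. The same amendment revised the number of sites and edited some eligibility criteria, and the chance of receiving active drug fell from 2/3 to 1/2. What is at stake is how a reader of the abbreviated report interprets the 3 mg and pooled lines. No type I error is involved.

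**Working it through.** **Inputs from the documents.** SAP 1.0: 34 subjects randomised. Protocol Appendix E: three equal arms before the change, so 1:1:1. SAP 2.3: 1:1 afterwards. SAP 2.4: "treatment difference of -8.3 between 6 mg/day and placebo" and "common standard deviation of 20 at Week 6 taking into account dropout rates and correlation matrix".

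**The plan's own figure.** SAP 2.4 states that "the sample size of 125 subjects per arm (N = 250) can achieve at least 90% power". With a difference of 8.3, SD 20 and two-sided alpha 0.05, the normal formula gives 123 per arm for 90% power, and 125 per arm gives 90.7%. The figure reproduces if there is no loss to dropout. The dropout and correlation inputs are not given, so I take nothing further from it. I use SD 20 below for interval widths.

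**Assumption.** The split of the 34 between stages is not reported. Let n1 be the number in stage 1 and n2 = 34 - n1. I show n1 = 9, 18 and 27.

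**Expected group sizes.** Placebo = n1/3 + n2/2. 3 mg = n1/3. 6 mg = n1/3 + n2/2. Pooled = 2n1/3 + n2/2.

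**Bias.** Let D be the stage 2 minus stage 1 difference in mean change, common to all arms. The expected bias of a raw difference is D × (stage 2 share of the cariprazine group - stage 2 share of placebo).

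For n1 = 18: placebo is 6 + 8 = 14, with stage 2 share 8/14 = 0.571. 3 mg is 6, with share 0. 6 mg is 14, with share 0.571. Pooled is 20, with share 8/20 = 0.400. The coefficients on D are:
- 3 mg: 0 - 0.571 = -0.571
- 6 mg: 0.571 - 0.571 = 0
- pooled: 0.400 - 0.571 = -0.171

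| n1 | Placebo / 3 mg / 6 mg | Stage 2 share, placebo | Stage 2 share, pooled | Part of D in 3 mg difference | Part of D in pooled difference | Part of D in 6 mg difference |
|---|---|---|---|---|---|---|
| 9 | 15.5 / 3 / 15.5 | 0.806 | 0.676 | 0.81 | 0.13 | 0 |
| 18 | 14 / 6 / 14 | 0.571 | 0.400 | 0.57 | 0.17 | 0 |
| 27 | 12.5 / 9 / 12.5 | 0.280 | 0.163 | 0.28 | 0.12 | 0 |

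The pooled coefficient never exceeds 0.171 in size for any split. A simulation at n1 = 18 with no treatment effect and an illustrative D of 5 points gave biases of -2.84 (3 mg), 0.04 (6 mg) and -0.82 (pooled). The formula gives -2.86, 0 and -0.86. The bias vanishes if D = 0 or if all 34 entered in one stage.

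**95% half-widths (SD 20, t distribution) at n1 = 18.**
- 3 mg versus all placebo: 20 × √(1/6 + 1/14) = 9.76; times t on 18 df gives 20.5 points.
- 3 mg versus concurrent placebo: 20 × √(1/6 + 1/6) = 11.55; times t on 10 df gives 25.7 points.
- Pooled, unstratified: 20 × √(1/20 + 1/14) = 6.97; times t on 32 df gives 14.2 points.
- Pooled, stratified: the stage variance factors are 1/6 + 1/12 = 0.25 and 1/8 + 1/8 = 0.25, combined 0.125; 20 × √0.125 = 7.07; times t on 31 df gives 14.4 points.

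**When does the concurrent 3 mg line have the smaller mean squared error?** It does when (0.571 D)² exceeds 11.55² - 9.76², about 38.1. That means D above 6.17/0.571, or 10.8 points. The same calculation gives 12.9 at n1 = 9 and 12.6 at n1 = 27.

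**The case against.** The strongest reply is that little depends on these contrasts. The primary and key secondary estimands in SAP Tables 1 and 2 are 6 mg/day versus placebo, allocated 1:1 in both stages. SAP 9.1 plans no tests, SAP 12.0 sets type I error control aside, and the pooled analysis is supplementary. That stands, and it is why the point is minor.

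Second, no document shows a shift in outcome. A reader might take "changes in the treatment environment with fewer relapses and exacerbations" in SAP 1.0, together with the pandemic mentioned there, as evidence of drift. The SAP offers these tentatively as reasons for slow enrolment. It does not say that PANSS change differed over time, nor does it place the changes between the two stages. Any number put on D is therefore illustrative.

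Third, restricting the 3 mg comparison to concurrent placebo buys lower bias with higher variance. On the assumptions above, it wins on mean squared error only for shifts beyond roughly 11 to 13 points, more than the planned effect of 8.3. This stands too, and argues for adding the concurrent line without dropping the planned one.

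Fourth, actual counts may depart from the expected fractions: randomisation is stratified by site, about 55 sites were planned (40 + 15), and only 34 subjects entered. Ethics approval of amendments (Protocol 8.1) may also have moved the switch date from site to site. Both are reasons to report the actual counts and to define stage by randomisation schedule, not by calendar date.

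None of this removes the mechanism. Descriptive status does not turn a partly non-concurrent comparison into a randomised one, and nothing in the SAP tells the reader of the difference.

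**Conclusion.** The point holds as a minor reporting and interpretation issue. If both stages enrolled, a between-stage shift in outcome enters the 3 mg difference at 28-81% of its size and the pooled difference at 12-17%, assuming 1:1:1 then 1:1 allocation and 9 to 27 of 34 subjects in stage 1. The 3 mg contrast carries most of the problem. For the pooled contrast, even an assumed 10-point shift would contribute at most about 1.7 points (0.171 × 10), against a half-width of about 14.

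Three stronger readings are not supported:
- That any calendar-time trend biases these contrasts. Drift within a stage does not enter in expectation, because the arms open in that stage are concurrent.
- That the primary comparison is compromised. The 6 mg contrast has a coefficient of zero.
- That the 3 mg comparison is wholly unrandomised. Some of its placebo subjects were randomised alongside it whenever stage 1 placebo subjects are in the analysis.

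Neither the stage sizes nor the size of any shift can be recovered from the documents.

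**What to change.** In SAP 9.1, keep the planned unstratified differences and add:

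1. 3 mg versus the placebo subjects randomised under the three-arm schedule, shown beside the planned 3 mg difference.
2. Pooled cariprazine versus placebo as a stage-stratified mean difference: the difference within each stage, combined with inverse-variance weights, beside the planned pooled difference.
3. A definition of stage as the randomisation schedule in force when the subject was randomised.
4. A table of n per arm per stage.
5. A sentence saying that the unstratified 3 mg and pooled contrasts include placebo subjects not randomised concurrently with 3 mg.

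If everyone proves to have been randomised in one stage, items 1 and 2 fall away and the table shows why.

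The cost is a few more outputs and, at 18 of 34 in stage 1 with SD 20, a half-width of 25.7 points on the concurrent 3 mg line against 20.5 on the planned line. With only 9 in stage 1 it would be 45.3 against 26.7, so that line may say little. The pooled half-width goes from 14.2 to 14.4. Stratifying also alters the dose mix slightly: at n1 = 18, 3 mg subjects are 6/20 = 30% of the unstratified pooled group, but carry 0.5 × 6/12 = 25% of the weight in the stratified difference. A footnote covers this.
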